
CRITERIA FOR EVALUATION
	
Primary efficacy endpoint: Progression-free survival (PFS) as assessed by the investigator.
 
Secondary endpoints
 
Efficacy endpoints:
 
 • PFS as assessed by independent centralized reading • Objective response rate (ORR; i.e., complete response [CR] + partial response [PR]) at the end of combination treatment • Best overall response rates (including maintenance therapy treatment) • Clinical benefit rate (CBR; i.e., CR + PR + stable disease [SD]) • Duration of response • Overall survival (OS) • Time to treatment failure (TTF) • QoL scores as assessed by European Oncology Research Trials Committee (EORTC) quality of life questionnaires (QLQ) EORTC-QLQ-C30 and EORTC-QLQ-H&N35. 
In addition, PFS and all secondary efficacy endpoints listed above will be analyzed by FcγRIIIa-allotype subgroups (i.e., FF, FV, and VV), by p16 status, by EGFR status, and other potential parameters, unless the sample sizes in subgroups are too low.
 
Pharmacokinetic endpoints: Antibody trough levels and PK profiles of CetuGEX™ will be assessed throughout the study.
 
Safety endpoints:
 
 • Incidence of adverse events (AEs) and serious AEs, including incidence of target/class-specific side effects (skin reactions, diarrhea) • IRRs • Physical and laboratory assessments • Vital signs • Electrocardiogram (ECG) 
In addition, the incidence of AEs will be analyzed by FcγRIIIa-allotype subgroups (FF, FV, VV).
 
Exploratory endpoints:
 
 • Immunogenicity: incidence of anti-drug antibodies (ADAs) • Immunological parameters: cytokine levels and immune cell status.

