5.3 Summary of Potential Risks and Benefits

As an optimized (bio-superior) second-generation antibody of the marketed product cetuximab, CetuGEX™ has the potential to become a considerably more active anti-EGFR antibody due to its significantly higher tumor-specific ADCC activity caused by the humanized and optimized glycosylation in the production process. At the same time the removal of non-human immunogenic Gal-Gal carbohydrate structures is expected to avoid the severe hypersensitivity reactions reported to be caused by non-human carbohydrate structures of cetuximab (in some geographical regions in about 22% of patients treated with cetuximab). Furthermore, CetuGEX™ opens the chance of therapeutic activity in otherwise unsuitable patients. As the key anti-tumor mode of action, ADCC is expected to be not only pronounced in patients with Fc γ RIIIa receptor allele status VV (8 - 27 % of the population) but also in those with FF and FV allotypes (73 - 92 % of the population), while the latter show no or very low anti-tumor ADCC activity with cetuximab. Therefore extended patient populations may benefit from the potential anti-tumor activity of CetuGEX™ in the clinic. The well-known cutaneous

toxicity occurring in up to 90% of patients treated with the approved anti-EGFR antibodies cetuximab and panitumumab (Vectibix®) is clearly linked to the EGFR inhibition in the skin and correlates with the anti-tumor efficacy of the antibody. This was also observed in the patients treated with CetuGEXTM, although from first evidence with lower incidence and grade. The phase 1 study showed reasonable tolerability with an expected high incidence of IRRs (mostly grades 1 and 2, few grade 3 and no grade 4) in conjunction with a considerable activity, given the far advanced cancer population.

Immediate allergic infusion reactions are unlikely; however IRRs of low grade were very common with this compound. As in general, although it didn't happen in the reported study, any infusion reaction has the potential to occur as life threatening severe reaction like a hypertensive crisis associated with neurologic signs and symptoms, wheezing, oxygen desaturation, chest pain, headaches, rigors, and diaphoresis, cardiac emergencies, anaphylaxis, cytokine release syndrome, convulsions, or hypotension, monitoring for these events will be cautiously undertaken.

In conclusion, the benefit-risk balance is deemed positive.

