### 2.2.2 *Safety Variables*

The safety endpoints are:

- Incidence of adverse events (AEs) and serious AEs (SAEs), including incidence of target/class-specific side effects (skin reactions, hypomagnesemia, neutropenia, gastrointestinal AEs, liver enzymes increases, conjunctivitis, mucositis)
- Infusion related reactions (IRRs)
- Physical assessments
- Laboratory assessments
- Vital signs
- Electrocardiogram (ECG)
- Relationship of FcγRIIIa and FcγRIIIa-allotypes, occurrence of ADAs and PK parameters to safety endpoints

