### **10.1.3 Adverse Events of Special Interest**

The times to the first occurrence of neutropenia (CTC-grade  $\geq 3$ ), liver enzymes increases (CTC-grade  $\geq 3$ ), (hypomagnesemia (CTC-grade  $\geq 3$ ), skin reactions (SOC="Skin and subcutaneous tissue disorders"), gastrointestinal symptoms (SOC="Gastrointestinal disorders), mucositis (PT="Mucositis") and conjunctivitis (PT="Conjunctivitis") will be investigated by Kaplan-Meier methods. Patients who did not experience this AE will be censored at the Safety Follow-up visit.

Logistic regression models including the CetuGex plasma concentration after the 3rd infusion as continuous covariable will be fitted to the incidences of AEs of special interest. Separate analyses will be performed for each of the AEs. Odds ratios, the corresponding 95%-confidence intervals and the p-values of the Wald test will be presented. Moreover, sample statistics of the CetuGex plasma concentration after the 3rd infusion grouped by the occurrence of these AEs (yes/no) will be presented including p-values of the Wilcoxon rank test.

AEs of special interest will be omitted from these analyses if their overall incidence is < 5%.

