## **12. CHANGES COMPARED TO THE CLINICAL TRIAL PROTOCOL**

All planned statistical analyses are in agreement with the clinical trial protocol.

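### SAP 10.1.3 replaces protocol-named diarrhea with the whole gastrointestinal SOC and sets no grade limit for skin, so its adverse-event Kaplan-Meier and concentration analyses can dilute a diarrhea signal and cannot show a difference in skin grade

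*Protocol*

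**What the plan says.** The protocol names two target or class effects in its safety endpoints: "including incidence of target/class-specific side effects (skin reactions, diarrhea"). The same pair appears in the Synopsis and in Protocol 7.1.2 and 13.1.4. The endpoint is incidence.

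SAP 2.2.2 gives a different list: "skin reactions, hypomagnesemia, neutropenia, gastrointestinal AEs, liver enzymes increases, conjunctivitis, mucositis". Diarrhea is not named.

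SAP 10.1.3 then defines the events of special interest in three ways:
- **Grade limit.** "The times to the first occurrence of neutropenia (CTC-grade" ≥ 3) opens the list. Liver enzyme increases and hypomagnesemia have the same limit.
- **Whole SOC, any grade.** "skin reactions (SOC='Skin and subcutaneous tissue disorders'), gastrointestinal symptoms (SOC='Gastrointestinal disorders), mucositis" and onward: skin and gastrointestinal events are complete System Organ Classes with no grade limit.
- **Single Preferred Term.** Mucositis and conjunctivitis.

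Times to first occurrence "will be investigated by Kaplan-Meier methods". No log-rank test is named. The same events are outcomes in logistic models on the CetuGEX concentration after the third infusion, and concentrations are compared between patients with and without the event by Wilcoxon test. Events with an overall incidence below 5% are left out. The outputs are Tables 14.3.3.5.1 to 14.3.3.5.3.

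SAP 12 states: "All planned statistical analyses are in agreement with the clinical trial protocol".

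**The concern.** SAP 10.1.3 already uses two ways to sharpen an event definition, a grade limit and a single Preferred Term. It applies neither to the two effects that the protocol singles out.

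For diarrhea, time to first event in a SOC counts only the earliest event of any kind in that SOC. Both arms are planned to receive cisplatin and 5-FU, so a patient may enter the curve through a different gastrointestinal event, and a diarrhea difference between arms is diluted. The same applies to the relation between concentration and diarrhea.

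For skin, Protocol 5.3 says of the approved antibodies that skin "toxicity occurring in up to 90% of patients treated with the approved anti-EGFR antibodies", and reports early evidence that both incidence and grade are lower with CetuGEX. A first any-grade event can reflect incidence and onset but not grade. Grade 3 is also the level at which Protocol 9.9 ties antibody dose changes to skin toxicity, and no time-to-event or concentration analysis addresses it.

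At stake is the reading of a secondary safety analysis: similar gastrointestinal curves, or a flat concentration relation, could be taken as reassurance about diarrhea when they say little about it.

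**Working it through.** **Plan's own figure.** The documents size no safety analysis. The only sizing figure is 192 PFS events (Protocol 13.2, SAP 5). With HR = 5.6/8.4 = 0.667, two-sided 0.05 and 80% power, the Schoenfeld formula gives 4 × (1.960 + 0.842)² / (ln 0.667)² = 191, within 3% of 192. The same formula is used below.

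**Inputs.** From the documents: about 240 patients, 1:1, taken as 120 per arm; skin toxicity in up to 90% with approved antibodies. Assumed, because the documents give no such rates: diarrhea 15% v 30%, and the share b of patients with another gastrointestinal event, 50% to 95%.

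**Formulas.**
- SOC rate = 1 − (1 − b)(1 − d), where d is the diarrhea rate and the two are independent.
- Under proportional hazards, HR = ln(1 − p_low) / ln(1 − p_high).
- Expected events D = 120 × (p_low + p_high).
- Log-rank power = Φ(|ln HR| × √D / 2 − 1.96).

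**Diarrhea alone.** HR = ln 0.85 / ln 0.70 = 0.456 and D = 120 × 0.45 = 54. Power = Φ(0.786 × 7.348 / 2 − 1.96) = Φ(0.93) = 82%. A comparison of the two proportions gives 80%.

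**Diarrhea inside the SOC.**

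| Other GI event (b) | SOC rates | HR | Log-rank power |
|---|---|---|---|
| 50% | 57.5% v 65.0% | 0.815 | 24% |
| 70% | 74.5% v 79.0% | 0.876 | 14% |
| 80% | 83.0% v 86.0% | 0.901 | 11% |
| 90% | 91.5% v 93.0% | 0.927 | 8% |
| 95% | 95.75% v 96.5% | 0.942 | 7% |

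With diarrhea at 20% v 35% the pattern is the same: 76% alone, then 24%, 15%, 12%, 8% and 7%. Most of the signal is already lost at b = 50%, so the point does not need gastrointestinal events to be near-universal.

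**Skin, any grade, control at 90%.**

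| CetuGEX rate | Chi-square power | Log-rank power |
|---|---|---|
| 85% | 21% | 29% |
| 80% | 58% | 72% |
| 75% | 87% | 95% |
| 53% | over 99% | over 99% |

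The 53% row adds the phase 1 rates for acneiform dermatitis (25%) and rash (28%) in Protocol 5.2, as if no patient had both. Those are related single terms from another setting and serve only as a guide. A large difference in any-grade skin incidence would show. What the analysis lacks is grade.

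Because SAP 10.1.3 names no log-rank test, these powers measure how much information the event definition discards. They do not forecast a planned test. The dilution in the logistic models follows from the same outcome definition and was not quantified.

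**The case against.** The strongest reply is that the protocol asks for incidence, and the SAP delivers it. SAP 10.1 tabulates TEAEs by arm at Preferred Term level, by maximum CTC grade and by relationship. SAP 15.1 lists the incidence and maximum-grade tables overall and separately for combination and maintenance treatment. Diarrhea at 15% v 30%, or a difference in grade ≥ 3 skin events, would be visible there. This stands, and it limits the point to onset over time and the relation to concentration, which those tables do not give.

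A reader might infer that nearly every patient will have an event in both SOCs, so that the curves cannot separate the arms. The documents do not support this. They give no rate for the gastrointestinal SOC. The figure of up to 90% for skin concerns the approved antibodies, with a lower incidence suggested for CetuGEX. A high event share does not disable a time-to-event comparison either: with 90% to 95% of 240 patients having an event, an HR of 0.68 to 0.69 is detectable with 80% power.

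A reader might also infer that diarrhea has no time-to-event comparison at all. SAP 11.6 plans time to a 10-point deterioration on the QLQ-C30 scales, including the diarrhea item, with a log-rank test. It is patient-reported at few visits, so it does not replace the adverse-event analysis.

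Lastly, a diarrhea term would not isolate an antibody effect, since Protocol 9.9.4 links grade 3 diarrhea to 5-FU dosing. That is correct, but both arms receive 5-FU, and the term is still closer to what the protocol names than the whole SOC.

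**Conclusion.** The point holds within limits. The SAP changes the protocol's list of class effects without saying so, and defines gastrointestinal and skin events more loosely than every other event in the same section. For diarrhea the loss can be large: in the illustration, 82% power falls to between 24% and 7%. That rests on assumed rates, independence of diarrhea from other gastrointestinal events, proportional hazards and 120 patients per arm. For skin the gap is one of kind: time to first any-grade event cannot show lower grade, whatever its power on incidence.

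The consequence is confined to the Kaplan-Meier, logistic and Wilcoxon analyses of SAP 10.1.3. The protocol's incidence endpoint and the primary PFS analysis are unaffected. This is a modest correction to a secondary safety analysis.

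**What to change.** - In SAP 10.1.3, add diarrhea as a Preferred Term (any grade and grade ≥ 3) and grade ≥ 3 events in the skin SOC to the Kaplan-Meier, logistic and Wilcoxon analyses.
- Let the existing 5% omission rule apply to the new rows.
- Keep the any-grade SOC analyses as supportive.
- Name diarrhea in SAP 2.2.2.
- Record the changed list of class-specific effects in SAP 12.

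The cost is SAP wording, a few extra rows in Tables 14.3.3.5.1 to 14.3.3.5.3 and a few more exploratory p-values. No new data are needed, because adverse events are already coded to Preferred Term and graded.

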4 LIST OF ABBREVIATIONS

ADA	Anti-drug antibody
ADCC	Antibody dependent cell cytotoxicity
ADR	Adverse drug reaction
AE	Adverse event
AUC	Area under the curve
BMI	Body mass index
BSA	Body surface area
BUN	Blood urea nitrogen
CBR	Clinical benefit response
CR	Complete response
CRA	Clinical research associate
CSR	Clinical study report
CT	Computed tomography
CTC	Common Toxicity Criteria
DSMB	Data safety monitoring board
ECG	Electrocardiogram
ECHO	Echocardiogram
eCRF	Electronic case report form
EDC	Electronic data capture
EGFR	Epidermal growth factor receptor
EORTC	European Oncology Research Trials Committee
FcγR	Fc-gamma receptor
FDA	Food and Drug Administration
GCP	Good Clinical Practice
GMP	Good Manufacturing Practice
HIV	Human immunodeficiency virus
IB	Investigator's Brochure
IgG	Immunoglobulin G
ICF	Informed consent form
ICH	International Conference on Harmonisation
IEC	Independent Ethics Committee
IMP	Investigational medicinal product
IND	Investigational New Drug
IRB	Institutional Review Board
IRR	Infusion-related reaction
irRC	Immune-related response criteria
ITT	Intention-to-treat
IWRS	Interactive web response system
KRAS	Kirsten rat sarcoma viral oncogene
MedDRA	Medical Dictionary for Regulatory Activities
MRI	Magnetic resonance imaging
MUGA	Multiple gated acquisition scan

nIMP	Non-investigational medicinal product
NCI	National Cancer Institute
NYHA	New York Heart Association
ORR	Objective response rate
OS	Overall survival
PD	Progression disease
PFS	Progression-free survival
PK	Pharmacokinetic
PP	Per-protocol
PR	Partial response
QLQ	Quality of life questionnaire
QoL	Quality of life
RECIST	Response evaluation criteria in solid tumors
SAE	Serious adverse event
SAF	Safety population
SAP	Statistical analysis plan
SCCHN	Squamous cell carcinoma of the head and neck
SD	Stable disease
SmPC	Summary of product characteristics
TEAE	Treatment emergent adverse event
TTF	Time to treatment failure
UADR	Unexpected adverse drug reaction
5-FU	5-fluorouracil

5 INTRODUCTION

5.1 Background

Cetuximab (Erbix[®]) is a chimeric immunoglobulin G (IgG) 1 mouse-human antibody targeted against the extracellular domain of the epidermal growth factor receptor (EGFR) with high specificity and affinity and is produced in the murine myeloma cell line SP2/0. Cetuximab is approved and marketed for clinical use as a single agent or in combination with chemotherapy for the treatment of EGFR-expressing, KRAS-non mutated, metastatic colorectal cancer. Cetuximab is also approved for use in combination with radiation therapy for treating squamous cell carcinoma of the head and neck (SCCHN) or in combination with platinum-based chemotherapy and 5-fluorouracil (5-FU) for the treatment of recurrent and/or metastatic SCCHN.

CetuGEX[™] is an improved second-generation antibody, designed to fully retain the antigen binding properties of cetuximab, e.g., affinity, specificity and EGFR inhibition, and is improved by fully human glycosylation and glycosylation optimization in its anti-tumor efficacy mediated by antibody dependent cell cytotoxicity (ADCC) and its lack of potentially immunogenic carbohydrate chains in order to improve drug efficacy and to reduce side effects. To obtain the fully human and optimized glycosylation, CetuGEX[™] is produced in a cell line of the GlycoExpress[™] system. Improvement of ADCC-mediated anti-tumor efficacy against EGFR positive tumor cells was demonstrated in *in vitro* studies in comparison to cetuximab. Adverse effects are likely to be reduced since non-human carbohydrate structures of cetuximab which result from its rodent cell based production system do not occur on CetuGEX[™]. The Gal-Gal carbohydrate and also other non-human structures present on cetuximab such as the neuraminic acid NeuGc are potentially immunogenic and known to be responsible for hypersensitivity reactions following cetuximab therapy.

Glycotope GmbH intends to develop CetuGEX[™] in various tumor indications, based on target expression and patient experience starting in patients with recurrent/metastatic SCCHN.

5.1.1 Study Drug – Mode of Action

CetuGEX[™] specifically binds to the EGFR and acts as a competitive antagonist at the ligand binding site of EGFR. The antigen specificity is exactly the same as for cetuximab.

An increasing body of data from various anti-tumor antibodies, such as rituximab (MabThera[®]), trastuzumab (Herceptin[®]) and cetuximab, indicates that the ADCC activity is the key mode of action of therapeutic anti-tumor antibodies in patients. Glycosylation structure especially the absence of core fucose and the presence of bisecting GlcNAc within the antibody Fc part are known key structures for an increased ADCC activity. Core fucose is present and bisecting GlcNAc absent on the Fc part glycans produced in rodent systems such as CHO and SP2/0 as it is the case for cetuximab. Therefore, CetuGEX[™] was glyco-optimized to contain bisecting GlcNAc and largely reduced core fucose of Fc glycans in order to achieve improved ADCC activity in a fully human

glycosylation setting. *In vitro* assays show that glyco-optimization of CetuGEX™ leads to a higher binding affinity of the molecule to the Fc-gamma receptor IIIa (FcγRIIIa) on natural killer cells, thereby enhancing ADCC activity and probably broadening the subpopulations per indication benefitting from such an antibody.

Two allotypes of this receptor are known which have different affinities to human IgG1 depending on the glycosylation of the Fc tail of IgG1. While antibodies with core fucose such as rituximab, trastuzumab and cetuximab bind to the V allotype inducing some ADCC activity in homozygous patients, they show a strongly reduced binding to the F allotype with little or no ADCC activity in homozygous (FF) or heterozygous (FV) patients. Addition of bisecting GlcNAc and/or reduction of core fucose at the Fc part glycan results in an increase of the binding affinity to the FcγRIIIa and an increase in ADCC activity. This increase is most pronounced for F allele types thereby broadening the patient coverage for the ADCC-mediated anti-tumor effect of antibodies^{1, 2, 3, 4}. This is also reflected by studies showing that patients with the higher affinity FcγRIIIa V allotype (VV) have a better clinical outcome than those with the lower affinity FcγRIIIa F allotype^{5, 6, 7, 8}.

The key mode of action of ADCC-mediated killing is improved for CetuGEX™ compared to cetuximab as tested in human assay systems. The degree of ADCC increase depends on the FcγRIIIa polymorphism status of the effector cells. The ADCC increase compared to cetuximab is higher for effector cells from donors comprising the FcγRIIIa F variant (~50-fold on FF, ~20-fold on FV) than for effector cells being homozygous for the V variant (~10-fold on VV). By achieving a ~10-fold improvement of anti-tumor ADCC activity with homozygous FcγRIIIa V alleles (the one best working for cetuximab) CetuGEX™ even reaches comparable absolute tumor cell killing rates with all receptor variants including the F allotypes. Thereby, the suitable patient spectrum is potentially broadened by making effective anti-tumor ADCC activities available also for the 80% of the patients bearing the lower affinity FcγRIIIa (FV and FF).

It is expected that due to improved ADCC activity for all FcγRIIIa allotypes CetuGEX™ will show comparable anti-tumor activity against tumor cells largely independent on KRAS status (KRAS wild types and mutants) because the downstream effector mechanisms mediated by EGFR are less relevant for the therapeutic effect.

5.1.2 GlycoExpress™ (GEX™)

The anti-tumor activity of cetuximab was improved manifold by glycolization-optimization using the proprietary production system GlycoExpress™ (GEX™). GlycoExpress™ is a toolbox consisting of a series of newly developed human glyco-engineered cell lines biotechnologically optimized not only for product optimization but also for high yield protein expression and fully reproducible quality from batch to batch. The GlycoExpress™ system is fully serum and virus free and well documented, rendering it suitable for pharmaceutical production. Three antibodies and 1 non-antibody manufactured using GlycoExpress™ are currently being tested in human clinical studies.

5.2 Clinical Experience

A phase 1 study has been performed at 5 sites in Germany, Italy and Switzerland. This was a dose escalation, multicenter study evaluating the safety, tolerability and pharmacokinetics of CetuGEX™ after intravenous administration in patients with locally advanced and/or metastatic solid cancers. The effect of CetuGEX™ on the development of anti-drug antibodies and on tumor response was also evaluated. This was an open-label, dose-escalation study in a 3 + 3 design, in which 3 to 6 eligible patients were enrolled into each of the sequential ascending dosing cohorts. CetuGEX™ was administered in 500 ml physiologic saline solution by intravenous infusion over a 2 or 3 hour-period, later amended to a more complex scheme.

Until the relevant cut-off date for the clinical study report, 40 patients were treated on a weekly (8 dose levels from 12 to 1370 mg flat dose), or once-every-two-weeks (990 mg flat) schedule. Twenty-four patients had received at least 8 weekly doses and were thus evaluable for activity. The most frequently observed related treatment-emergent adverse events (TEAEs), all grades, apart from infusion related reactions (IRRs), were acneiform dermatitis (25%), skin rash (28%), asthenia (15%), fatigue (13%) and nausea (10%). Observed IRRs, all grades, (70%), virtually restricted to the first infusion and most of mild or moderate grade, were associated with cytokine secretion: IL-6, IL-8, TNF α , IFN γ and IP-10 as marker of macrophage activation. An optimized infusion scheme and premedication reduced the incidence of IRRs. Activity was seen over all dose levels. One patient with non-small cell lung cancer achieved a complete response. Another 2 patients with esophageal and gastric cancer without measurable disease at study entry had marked improvement of symptoms and normalization of tumor markers. Additional 15 patients had stable disease lasting from 8 weeks to over a year, including several minor responses, leading to a clinical benefit rate of 45% (18/40) in the overall and 75% (18/24) in the PP population. Pharmacokinetics (PK) supports weekly and bi-weekly dosing. One additional patient was included into the study after the cut-off date and results of this patient are not yet included within the summary presented above.

